## **9.6 Interim Analysis**

The timing of interim analysis will be based on rate of patient accrual. An initial interim analysis will be performed after 10 patients are randomized in each arm. Futility and efficacy will be assessed in each treatment arm by calculating Bayesian posterior probabilities. The beta distribution for the efficacy/success rate is utilized with a non-informative Jeffrey's prior equal to beta (0.5, 0.5). Specifically, a futility rate  $\leq$  80% will be assumed and the probability for stopping for futility will be set at 70%. An efficacy rate  $\geq$  90% will be assumed and a

probability for early stopping for efficacy set at 90%. Based on these assumptions, the futility stopping boundary for the first 10 patients in each arm is set at  $\leq 7$  patients with clinical stability (i.e. less than 2 point decrease in COVID 7-POINT ORDINAL SCALE) in a specific treatment arm.

The Bayesian methodology allows flexibility in the timing and cohort size in each arm in the conduct of each interim analysis. Thus, depending on patient enrollment and cohort size in each arm, subsequent interim analyses will be performed (e.g. after every 10 additional patients in each arm) and additional stopping bounds will be calculated. ***Real-time assessments of patient response will be critical and will be facilitated by close coordination of clinical and research teams.***

**The decision making process for this trial such as dropping an arm or other changes on how to proceed with the trial will be based on clinical and safety considerations along with newly developing information on COVID19 as well as guidance by results of efficacy estimates and interim posterior probabilities.**

## **10. ADVERSE EVENTS: LIST AND REPORTING REQUIREMENTS**

Adverse event (AE) monitoring and reporting is a routine part of every clinical trial. Adverse events must be evaluated by the investigator, graded and assigned an attribution of relatedness to study treatment. The characteristics of an observed AE will determine whether the event requires expedited reporting to Overall PI, the FDA, the UK IRB, and MCC DSMC via **in addition** to routine reporting.

### **10.1 Evaluation of Toxicity**

All patients will be evaluable for toxicity from the time of their first treatment with the investigational agents described above.

### **10.2 Adverse Event Characteristics**

Adverse events (AEs) will be summarized by presenting, for each arm, the number and percentage of patients having any AE, having an AE in each MedDRA primary system organ class (Appendix G) and having each individual AE (preferred term) including relatedness. Additionally, a summary of adverse events by preferred term and severity will be performed using the worst severity grade.

All AEs must be evaluated and commented on by the Investigator and graded according to the DMID Toxicity Scale for Determining Severity of Adverse Events ([Appendix G](#)).

All related AEs, AEs with outcome death, AEs leading to permanent discontinuation of treatment, SAEs and related SAEs will be summarized by percentages and frequencies and listed including the Investigator term, the preferred term, start and end date of AE, duration (days), severity, drug relationship, action taken and outcome.

- **Attribution** of the AE:

- Definite – The AE *is clearly related* to the study treatment.
- Probable – The AE *is likely related* to the study treatment.
- Possible – The AE *may be related* to the study treatment.
- Unlikely – The AE *is doubtfully related* to the study treatment.
- Unrelated – The AE *is clearly NOT related* to the study treatment.

### 10.3 MCC Expedited Adverse Event Reporting Guidelines

Investigators will report SAEs that are possibly, probably or definitely related to study drug or procedures directly to the MCC DSMC per the MCC DSMC SOP and the University of Kentucky IRB reporting policy, as specified below. Use the MCC protocol number and the protocol-specific patient ID assigned during trial registration on all reports.

In addition to reporting to IRB, MCC DSMC and the PI, for agents under an IND, investigators will report all medication related (possibly, probably or definitely related) SAEs to the FDA per required reporting processes using MedWatch form 3500. In summary:

1. During phase I run in period, report grade 1-5 adverse events (AEs) that are drug-related (possibly, probably or definitely related) to PI, IRB, DSMC in an expedited fashion. Following phase I run-in period for each arm, report grade 3-5 SAEs that are drug related to PI, IRB, DSMC. After the phase I run-in period, grade 1 and 2 AEs related to FDA approved medications or botanical products are only reported if determined by the investigator to be clinically significant AEs.
2. Report any unexpected fatal or life-threatening suspected adverse reactions to the FDA no later than 7 calendar days after initial receipt of the information. Submit 7-day reports electronically in eCTD format via the FDA Electronic Submissions Gateway (ESG).
3. Report any serious, unexpected suspected adverse reactions or a clinically important increase in the rate of a serious suspected adverse reaction to the FDA electronically in eCTD format via the ESG and to all investigators no later than 15 calendar days after determining that the information qualifies for reporting.

**Do not report COVID-19 AEs or other AEs to these entities unless they are related to study medication or procedures as listed above.**

**Note: A death on study requires both routine and expedited reporting, regardless of causality. Attribution to treatment or other cause must be provided.**

**Expedited Reporting Requirements for Adverse Events that Occur on Medications in Study Arms under an IND/IDE within 30 Days of the Last Administration of the Investigational Agent/Intervention**


FDA REPORTING REQUIREMENTS FOR SERIOUS ADVERSE EVENTS (21 CFR Part 312)  NOTE: Investigators MUST immediately report ANY Serious Adverse Events, as listed below(21 CFR 312.64)                  An adverse event is considered serious if it results in ANY of the following outcomes:
 
 
1) Death
 
2) A life-threatening adverse event
 
3) An adverse event that results in inpatient hospitalization or prolongation of existing hospitalization for ≥ 24 hours
 
4) A persistent or significant incapacity or substantial disruption of the ability to conduct normal life functions
 
5) A congenital anomaly/birth defect.
 
6) Important Medical Events (IME) that may not result in death, nor be life-threatening, nor require hospitalization may be considered serious when, based upon medical judgment, they may jeopardize the patient or subject and may require medical or surgical intervention to prevent one of the outcomes listed in this definition. (FDA, 21 CFR 312.32; ICH E2A and ICH E6).
 
		

ALL SERIOUS adverse events that meet the above criteria MUST be immediately reported via electronic submission within the timeframes detailed in the table below.
		
Hospitalization	Grade 1 and Grade 2 (definite, possibly or probably related to study medication) Timeframes	Grade 3-5 (definite, possibly, or probably related to study medication) Timeframes
Resulting in Hospitalization ≥ 24 hrs	10 Calendar Days	24-Hour; 5 Calendar Days
Not resulting in Hospitalization ≥ 24 hrs	Not required	

NOTE: Protocol specific exceptions to expedited reporting of serious adverse events are found in the Specific Protocol Exceptions to Expedited Reporting Section.
 
Expedited AE reporting timelines are defined as:
 
 
○ “24-Hour; 5 Calendar Days” - The AE must initially be submitted electronically within 24 hours of learning of the AE, followed by a complete expedited report within 5 calendar days of the initial 24-hour report.
 
○ “10 Calendar Days” - A complete expedited report on the AE must be submitted electronically within 10 calendar days of learning of the AE.
 
		

Serious adverse events that occur more than 30 days after the last administration of investigational agent/intervention and have an attribution of possible, probable, or definite require reporting as follows:  Expedited 24-hour notification followed by complete report within 5 calendar days for:
 
 
• All Grade 3, 4, and Grade 5 AEs
 
 
Expedited 10 calendar day reports for:
 
Grade 1 and 2 AEs resulting in hospitalization or prolongation of hospitalization
		

#### **10.4 Exceptions to AE reporting**

Adverse events related to SARS-CoV-2 infection are exempt from adverse event reporting unless the investigator considers the event to be possibly, probably, or definitely related to the study drug or study procedures. Examples of COVID-19 related AEs include:

- Death not related to the study procedures
- Neurological events
  - Seizure
- Cardiovascular events
  - Atrial or ventricular arrhythmia
  - Cardiac arrest
- Respiratory events
  - Hypoxemia requiring supplemental oxygen
  - Acute respiratory distress syndrome
  - Receipt of mechanical ventilation
  - Receipt of extra-corporeal membrane oxygenation

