### 9.2 Secondary Endpoints

#### Secondary endpoints related to efficacy:

- Presence of symptoms or physical examination signs related to COVID-19 disease on Day 14 including: fever, shortness of breath, muscle aches, sore throat, loss of sense of taste or smell, etc.
- Presence of SARS-CoV-2 RNA as detected by polymerase chain reaction (PCR) in nasopharyngeal samples measured minimally on Days 1, 14 and 28
- Proportion of patients with symptoms or physical examination signs related to COVID-19 disease including shortness of breath, muscle aches, sore throat, loss of sense of taste or smell, hospital admission, length of stay, supplemental oxygen requirements, need for mechanical ventilation, intensive care unit admission, etc.

- Time to improvement and resolution of symptoms from baseline to Day 14 and 28
- Oxygen-free days to Day 28
- Ventilator-free days to Day 28
- Vasopressor-free days to Day 28
- ICU-free days to Day 28
- Hospital-free days to Day 28

#### Secondary endpoints related to safety and tolerability up to Day 28

- Incidence, severity, drug-relatedness, and seriousness of adverse events
- Proportion of patients meeting Hy's law criteria
- Proportion of patients with the following Liver function tests (LFT) changes:
  - Any ALT or AST  $\geq 5 \times$  ULN
  - Any AST or ALT  $\geq 3 \times$  ULN together with the appearance of fatigue, nausea, vomiting, right upper quadrant pain or tenderness, fever, rash and/or eosinophilia (eosinophil percent or count above the ULN)
  - Persistent ALT  $\geq 3 \times$  ULN for a period of more than 4 weeks.
- Proportion of patients with significant changes in ECG findings, including heart rate, ECG intervals (PR, QTcB, QTcF), conduction changes, or abnormalities including severe QTc prolongation of  $> 500$  ms.
- Proportion of patients with serious allergic and skin reactions
- Proportion of patients with severe hypoglycemia
- Proportion of patients with retinopathy or macular degeneration
- Proportion of patients with seizure
- Proportion of patients with acute pancreatitis
- Proportion of patients with acute kidney injury
- Proportion of patients with receipt of renal replacement therapy
- Proportion of patients with neutropenia, lymphopenia, anemia, or thrombocytopenia
- All-cause mortality rate

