#### **10.8 Routine Adverse Event Reporting**

All Adverse Events that are definitely, probably or possibly related to study treatment **must** be reported in routine study data submissions with the exception of those listed in Section 10.4. **AEs reported expeditiously to the Overall PI and DSMC must also be reported in routine**

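### The adverse event reporting rules in 10.3, 10.4 and 10.8 contradict each other and section 6.1, and do not supply the data that the safety summaries in 9.2 and 10.2 need

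*Combined protocol and SAP*

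**What the plan says.** Section 10.4 sets the exemption: "Adverse events related to SARS-CoV-2 infection are exempt from adverse event reporting". It is lifted only where the investigator judges a link with study treatment or procedures to be at least possible. Its examples include "Death not related to the study procedures", seizure, "Atrial or ventricular arrhythmia", cardiac arrest, and respiratory events up to mechanical ventilation and ECMO.

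Section 10.8 says that AEs at least possibly related to treatment must "be reported in routine study data submissions with the exception of those listed in Section 10.4". It adds that low-grade (1 and 2) events on certain named agents need reporting only if the investigator finds them clinically significant.

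The safety endpoints in section 9.2 include "Proportion of patients with seizure" and "All-cause mortality rate". They also cover how often AEs occur, how severe and serious they are, and whether the drug caused them. None of these carries an attribution condition. Section 10.2 plans tables of any AE with relatedness, of fatal AEs, and of all SAEs separately from related SAEs. Its attribution scale runs from definite down to unrelated.

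On deaths, section 10.3 says: "A death on study requires both routine and expedited reporting, regardless of causality". The sentence just before that note tells investigators not to send COVID-19 AEs to the oversight bodies unless they are related.

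Section 6.1 says that hospitalizations and all complications go on AE case report forms. Section 12.2 takes mortality and grade 3 or greater non-hematologic events from medical records.

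**The concern.** A safety table of incidence needs every event, with the investigator's view of cause recorded as a variable. Sections 10.4 and 10.8, followed literally, make that view the condition for an event entering the routine data.

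That filter is weak in this trial. Section 4.9 has arm assignments sent to the study team, and the blinding in section 9.4 covers only the randomization lists, so the person judging cause knows the drug. Section 9.1 rules out a placebo or between-arm comparison, so there is no comparator rate to show misattribution. Seizure and arrhythmia can come from the disease or from a drug, and section 6.1 says that safety data for these drugs are lacking in this population.

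The plan also gives sites conflicting instructions. Two coordinators who each follow a section faithfully could fill the AE data differently.

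**Working it through.** No arithmetic applies, so the check sets the passages side by side.

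**1. How far the exemption reaches.** Section 10.4 speaks of AE reporting without limiting this to expedited reports. Section 10.8 then applies the exception to routine data submissions. It therefore affects data meant for analysis as well as notices to the IRB, DSMC or FDA.

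**2. What the cross-reference does.** Section 10.8 starts from related AEs and removes those in 10.4, but 10.4 exempts an event only when it is not judged related. Read together, the exception removes nothing, and the restriction to related events in 10.8 does the work. That restriction also leaves out unrelated AEs that have nothing to do with COVID-19. If the 10.4 list is read as event types instead, a possibly related seizure would drop out too, against the condition in 10.4 itself.

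**3. Planned outputs against available data.**

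| Planned output | Supplied under 10.8 | Other source in the plan |
|---|---|---|
| Any AE, with relatedness (9.2, 10.2) | Related AEs, plus deaths if 10.3 is followed | AE forms, if 6.1 is followed |
| All SAEs beside related SAEs (10.2) | Related SAEs, plus deaths if 10.3 is followed | Medical records for grade 3 or greater non-hematologic events (12.2); AE forms (6.1) |
| Seizure (9.2) | Only those judged at least possibly related | Medical records: Appendix G treats seizure as grade 4, inside the 12.2 threshold |
| All-cause mortality (9.2) | All under 10.3; not COVID-attributed deaths under 10.4 | Level 1 of the ordinal scale (Appendix B); medical records (12.2) |
| ECG changes (9.2) | Only those judged at least possibly related | Day 14 EKG; medical records for grade 3 or greater |
| Grade 1-2 or unrelated AEs (9.2, 10.2) | Unrelated: none. Related grade 1-2: partly | 6.1 only, so far as the event counts as a complication |

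The last row has the thinnest cover. For example, a grade 2 rhythm event under Appendix G is transient and asymptomatic, so it falls below the 12.2 threshold. The Day 14 EKG sees it only if it is present then.

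**4. Low-grade events by arm.** The clinical-significance filter in 10.8 names ivermectin and Artemisia annua but not camostat or artesunate. Collection of related grade 1-2 events would therefore differ between arms that section 9.5 tabulates in the same way.

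**5. Deaths.** A death attributed to COVID-19 needs routine and expedited reporting under the 10.3 note but is listed as exempt in 10.4. The 10.4 bullet mentions study procedures and not study drug, although the sentence introducing the list covers both.

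**The case against.** The strongest reply is that reporting is not recording. Section 6.1 puts complications on AE forms. Section 10.2 requires every AE to be evaluated and graded, with unrelated as an available category. The study calendar has a continuous AE row, and section 13.6 has the DSMC reviewing all AEs. The threshold for losing the exemption is also low, since a possible link is enough. Several exempt items, such as oxygen and ventilation, are already efficacy outcomes, so not reporting them again as AEs is understandable. The 10.3 death note is specific and can be read as overriding 10.4.

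Much of this stands, and it limits the point. A reader might infer that COVID-attributed deaths and seizures would disappear from the trial, that the AE data would show no deaths, or that every AE would be drug-related by construction. The documents do not support this. Deaths are counted through the ordinal scale, medical records and the 10.3 note. Seizure is reached by the 12.2 record review. Sections 6.1 and 10.2 provide for unrelated events.

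The reply does not remove the contradiction. Section 6.1 conflicts with 10.8 and nothing says which prevails. Section 12.2 stops at grade 3 non-hematologic events. Neither section says what is submitted as routine data.

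**Conclusion.** The AE rules are internally inconsistent and do not match the planned safety analysis. Section 10.8 with 10.4 would filter the AE tables by attribution made with knowledge of the arm, while 6.1, 9.2 and 10.2 assume unfiltered data. The death bullet in 10.4 conflicts with 10.3.

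The exposure is moderate. It falls mainly on the AE incidence and relatedness tables, on lower-grade and unrelated AEs, and on what sites are to submit. Mortality is the least exposed endpoint. Seizure is partly protected by the record review.

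No numerical size should be attached. It may be tempting to multiply the case-fatality range in section 2.1 by the arm size. That range is general, and the same sentence says fatality is higher with comorbid conditions, which section 3.1.3 enrolls, while section 3.2 excludes severe disease. The product would also not measure lost data, because deaths are found by other routes.

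The conclusion assumes that sites would follow 10.4 and 10.8 as worded. If they follow 6.1 and submit everything, the tables can be filled, but the plan does not tell them to.

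**What to change.** Three wording changes are needed.

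- In 10.4, limit the exemption to expedited reporting.
- In 10.8, require every AE to be recorded and submitted in routine study data, with attribution as a field, consistent with 6.1, 9.2 and 10.2. Remove the circular reference to 10.4, and reconcile the grade 1-2 sentence so that all arms are collected alike. That sentence needs editing anyway, because it still names hydroxychloroquine and azithromycin, which are no longer study arms.
- Reconcile the 10.4 death bullet with the 10.3 note, so that deaths follow one rule throughout section 10. The endpoints in 9.2 and the fatal-AE listing in 10.2 need every death in the routine data.

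The cost is more CRF entry, chiefly for low-grade and COVID-attributed events. No new visits or procedures are required.

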#### **10.5 Expedited Reporting to External Agencies**

Overall PI will comply with the policies of all external funding agencies and the UK IRB regarding expedited reporting, as per the UK IRB's Mandated Reporting to External Agencies SOP C4.0150.

#### **10.6 Expedited Reporting to the Food and Drug Administration (FDA)**

Overall PI, as study sponsor, will be responsible for all communications with the FDA. The Overall PI will report to the FDA, regardless of the site of occurrence, any serious adverse event that meets the FDA's criteria for expedited reporting following the reporting requirements and timelines set by the FDA using the MedWatch 3500 form by one of the following means:

- To fax report: [name]
- To report online: [www.fda.gov/medwatch/report.htm](http://www.fda.gov/medwatch/report.htm)
- To report by email: [[contact]](mailto:[contact]).

#### **10.7 Expedited Reporting to Hospital Risk Management**

Participating investigators will report to the UK Office of Risk Management any participant safety reports or sentinel events that require reporting according to institutional policy.

#### **10.8 Routine Adverse Event Reporting**

All Adverse Events that are definitely, probably or possibly related to study treatment **must** be reported in routine study data submissions with the exception of those listed in Section 10.4. **AEs reported expeditiously to the Overall PI and DSMC must also be reported in routine**

**study data submissions.**

**Grade 1 and 2 adverse events related to FDA approved medications used in this trial (i.e. hydroxychloroquine, azithromycin, ivermectin, artemisia annua) are only reported if determined by the investigator to be clinically significant AEs.**

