## **9.5 Statistical Analysis Plan**

The primary analysis will include estimate of the rate of stability in clinical scale (less than 2 point decrease in COVID 7-POINT ORDINAL SCALE) for each arm along with exact binomial 90% confidence interval. This is based on the first response in clinical scale after enrollment and randomization into the trial. In addition, the Bayesian posterior probability of the response rate being greater than 90% will be calculated for each arm at the end of the trial. The rates of development of severe respiratory or organ failure, clearance of viral RNA at day 28 and mortality will be summarized in each arm. Changes in SARS-CoV-2 RNA as detected by polymerase chain reaction (PCR) over time will be summarized in each treatment arm and compared using paired tests or longitudinal linear models.

Secondary endpoints related to proportion of outcomes as indicated in Section 9.2 will be estimated along with exact confidence intervals while descriptive statistics including median, range, IQR will be calculated for the duration in days of efficacy outcomes. Survival analysis methods will be utilized to estimate time to event endpoints. The exploratory and correlative endpoints such as inflammatory markers and cytokine levels will be summarized at baseline and follow-up time points. Changes from baseline will be compared using paired test or longitudinal linear mixed models.

Secondary analyses will include estimates of rate and confidence intervals of stability in clinical scale (less than 2 point decrease in COVID 7-POINT ORDINAL SCALE) either from the outpatient or inpatient continuum using subgroup analyses or logistic regression with a variable to account for response status among outpatients for each arm.

All patients who received study drugs will be included in the safety analysis. The maximum grade of toxicity for each category of interest will be recorded for each patient and summary results will be tabulated by category and grade. We will describe all serious ( $\geq$  grade 3) toxicity events. Frequency and incidence tables of toxicity and AEs will be generated in each treatment arm. Likewise, proportions of specific safety endpoints in Section 9.2 will be summarized.

m-ITT population is defined as all patients who have been randomized and received at least one dose of the study treatment. The primary analysis will be based on the m-ITT population.

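### As written, Section 10.8 filters related grade 1–2 adverse events out of routine data for ivermectin and Artemisia annua but not for camostat or artesunate, and it conflicts with other recording rules

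*Combined protocol and SAP*

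**What the plan says.** Section 10.8 (Routine Adverse Event Reporting) opens with a general duty: "All Adverse Events that are definitely, probably or possibly related to study treatment" have to go into the routine data submissions, apart from the COVID-19 events exempted in Section 10.4. Anything sent as an expedited report must go into the routine data as well. The section's last sentence makes an exception. The events concerned are "Grade 1 and 2 adverse events related to FDA approved medications used in this trial (i.e. hydroxychloroquine, azithromycin, ivermectin, artemisia annua" (the list ends there), and these "are only reported if determined by the investigator to be clinically significant AEs". No criteria for that judgement are given.

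Section 6.1 lists four current regimens: ivermectin (C), camostat (D), Artemisia annua tea or coffee (E) and artesunate (F). Two of the four names in the 10.8 list are therefore no longer study drugs, and camostat and artesunate are not named.

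Section 10.3, on expedited reporting, has a related rule with a different scope. It begins: "During phase I run in period, report grade 1-5 adverse events (AEs) that are drug-related". After the run-in, "grade 1 and 2 AEs related to FDA approved medications or botanical products are only reported" subject to the same investigator judgement. This version is defined by category and limited in time; the 10.8 version is defined by name and has no time limit.

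The planned outputs do not distinguish arms or grades in this way. Section 9.5 states: "Frequency and incidence tables of toxicity and AEs will be generated in each treatment arm". Section 10.2 promises, for each arm, "the number and percentage of patients having any AE", with breakdowns by organ class, preferred term, relatedness and worst grade. Section 9.2 makes the incidence, severity and relatedness of adverse events a secondary endpoint.

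**The concern.** A by-arm table can be read side by side only if every arm's events enter it under the same rule. Here the filter stands in the routine-data section, so on its face it decides what reaches the study data as well as what is notified quickly. It applies to two of the four arms.

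The filter is an investigator's judgement without stated criteria. That judgement is not blinded: Section 9.4 withholds the randomization lists from most personnel, but Section 4.9 has each arm assignment sent to the study team.

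Safety, tolerability and compliance for each regimen is a secondary objective (Section 1.2.6), and in mostly outpatient treatment tolerability is largely a matter of grade 1–2 events. If arms C and E record fewer of them by rule, those arms look better tolerated for a reason unrelated to the drug. Events that were never entered cannot be restored at analysis.

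**Working it through.** The plan states no adverse event rate for these tables, so there is no figure of its own to reproduce. The check is a comparison of the passages, followed by an illustration of size.

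**Which rule applies to which arm**

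- Arms D and F: not named in 10.8, so all related events of every grade go into routine data.
- Arms C and E: named in 10.8, so related grade 1–2 events go in only if judged clinically significant.
- Run-in: 10.3 has related grade 1–5 events reported in an expedited way, and 10.8 sends expedited events into routine data. Read together, the run-in patients are fully captured in every arm. The 10.8 exception does not itself mention the run-in.
- Other passages: 6.1 has complications recorded on adverse event case report forms, 10.2 has every event evaluated and graded, and the Section 11 calendar shows events collected throughout. These apply to all arms and do not fit the 10.8 exception.

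**Size, if 10.8 governs the table data**

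Inputs from the documents: 60 patients per arm (9.3) and 6 run-in patients per arm (6.1 and 9.1). I assume the six count towards the 60, which leaves 54 exposed to the filter.

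Assumed inputs: *p*, the true proportion of patients with a related grade 1–2 event, equal in all arms; and *s*, the share of post-run-in patients with such an event in whom it is judged clinically significant.

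- Recorded rate in D and F: *p*
- Recorded rate in C and E: *p* × (6 + 54*s*)/60

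For *s* = 0.25 the multiplier is (6 + 13.5)/60 = 0.325. For *s* = 0.50 it is (6 + 27)/60 = 0.55.

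| True rate *p* | D and F record | C and E record, *s* = 0.25 | C and E record, *s* = 0.50 |
|---|---|---|---|
| 5% | 5% | 1.6% | 2.8% |
| 20% | 20% | 6.5% | 11.0% |
| 27.5% | 27.5% | 8.9% | 15.1% |

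At *p* = 20% this is 12 patients in each of D and F against an expected 3.9 to 6.6 in each of C and E, a gap of 9 to 13.5 percentage points. The 20% is purely an assumption. The 5% is the nausea or vomiting rate quoted for the tea in Section 2.4, and the 27.5% is the nausea rate quoted for artemisinin combinations in children in Section 2.5. Both come from malaria studies and serve only to mark a range.

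If 10.8 were read as having no run-in exception, the multiplier would be *s* itself, and the 20% row would become 5% to 10%. With one rule in all arms (*s* = 1) the multiplier is 1 and the gap is zero.

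The formula describes patients with a recorded related grade 1–2 event. In the any-event row the gap would be smaller where such patients also have another event that is recorded.

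**The case against.** The strongest reply is that reporting is not the same as recording. Sections 6.1, 10.2, 11 and 12.2 all point to events being collected on case report forms in every arm. Section 13.4.1 separates a minimal data set in OnCore from case report forms in REDCap. On that reading the tables could be built from complete forms, and the 10.8 exception would affect only what is passed on. The stale drug names also suggest a leftover sentence rather than a considered rule; the version 4 summary of changes lists Section 10.3 as updated but not 10.8.

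This has force. A reader might infer that the safety tables are certain to be biased, and the documents do not support that. They support a conflict whose consequence depends on which passage governs. The reply does not dispose of the point, however: 10.8 is the passage that sets the rule for routine study data, and nothing says the 9.5 and 10.2 tables draw on another source.

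Two other stronger readings also fail. A reader might test the illustrative counts against each other and report a p-value. Section 9.1 rules out hypothesis testing and comparisons between arms, the tables are descriptive, and the counts rest on assumed inputs. A reader might also infer that the distorted rates would decide which arm goes forward. Selection rests on the clinical stability rate (9.1 and 9.3). Section 9.6 refers to clinical and safety considerations in general, but no rule uses grade 1–2 rates.

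The category label in 10.3 does not settle matters either. Section 10.8 treats Artemisia annua as FDA approved while Section 2.4 calls it a botanical product, and Section 2.3 describes camostat as approved in the United States under an IND. Whether camostat falls under the 10.3 filter is therefore unclear, although 10.8 does not name it.

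**Conclusion.** The point holds in conditional form. As written, 10.8 removes related grade 1–2 events from routine data by unblinded judgement in arms C and E only, and it conflicts with 10.3 on timing and with 6.1 and 10.2 on completeness. If 10.8 governs the table data, C and E would appear better tolerated than D and F at equal true rates.

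The size depends on two quantities that the documents do not give. With a 20% true rate and 25–50% judged clinically significant, C and E would show about 6.5–11% against 20%. The gap is smaller at lower true rates, and vanishes if every such event is judged significant or if the tables use complete case report forms.

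The reach is limited to related, non-serious grade 1–2 events after the run-in. The dose-limiting toxicity rule, grade 3 or higher events, serious events and the primary endpoint are untouched, as are the laboratory and ECG endpoints in 9.2 if they are taken from measured values. The defect lies in the descriptive tolerability comparison and should be corrected, because the loss cannot be repaired at analysis.

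**What to change.** - In 10.8, require related adverse events of every grade to be entered on the case report form under one rule in all arms, for the whole reporting period.
- Confine any clinical-significance filter to expedited reporting in 10.3, and say there which current agents it covers.
- Delete the outdated drug list from 10.8.
- State in 9.5 and 10.2 that the by-arm tables use these case report form data.

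Extending entry to unrelated events is not needed to remove the difference between arms, since 10.8 requires only related events in any arm. If the sponsor prefers to keep the filter, restricting the by-arm tables to grade 3 or higher would avoid the artefact but give up most of the tolerability information.

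The cost is wording plus modest extra data entry, mainly in arms C and E. It is close to nil if the forms are already completed as 6.1 describes.
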